8.0 Study Calendar

Screening			Study Day					
Interventions	Phone	Interview	Before session	Baseline Block	OT/PL Block	Alcohol Clamp	Alcohol Self- administration	
Phone Screen	Х							
Liver Function panel		Х						
Medical History		Х						
UPPS-P Impulsive Behaviors Scale		Х						
Generalized Anxiety Disorder Assessment (GAD-7)		X						
Patient Health Questionnaire for depressive symptoms (PHQ-9)		X						

Alcohol Use Disorders Identification	Х					
Test (AUDIT)						
Semi-structured Assessment for the	Х					
Genetics of Alcoholism (SSAGA);						
Alcohol and Family History modules						
Self-Rating of Effects of Alcohol	Х					
(SRE).						
Short Inventory of Problems –	Х					
Revised (SIP-r)						
Clinical Institute Withdrawal	Х					
Assessment for Alcohol Scale (CIWA)						
Nicotine History (NHF)	Х					
Penn Alcohol Craving Scale (PACS)	Х					
Timeline Followback (TLFB) recall of	Х	Х				
alcohol and drug use						
Urine Pregnancy Screen (UPS)	Х	Х				
Urine Drug Screen (UDS)	Х	Х				
Breath Alcohol Concentration (BrAC)	Х	Х			Х	Х
Alcohol Purchase Task (APT)	Х		Х	Х	Х	
Stop Signal Response Task			Х	Х	Х	
Stroop Test			Х	Х	Х	
Subjective Perceptions Assessment			Х	Х	Х	Х
Side-Effects Questionnaire			Х	Х	Х	Х

9.0 Reportable Events

Serious adverse events resulting in any physical harm associated with testing will be reported to the IRB as required by applicable policies and guidance. Minor, and expected, adverse events (e.g. nausea, infusate infiltration, discomfort associated with infusion, nasal irritation) will be reported to the Alcohol Studies DSMB meeting at least annually. Side effects attributable to the interventions will be reported in any manuscripts or scientific reports based upon the collected data and entered into any mandated database.

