10.0 Data Safety Monitoring

The Data Safety and Monitoring Board (DSMB) that monitors virtually all the alcohol studies at IUSM will review this study at least annually. This board is comprised of all IU faculty engaged in IV alcohol research, and chaired by [name], who is independent of the sponsor and investigators. The following will be monitored as part of the Data Safety Monitoring Plan (DSMP): data quality, recruitment, accrual, retention, outcome and adverse event data, assessment of scientific reports or therapeutic development, results of related studies that may impact participant safety, and procedures designed to protect the privacy of participants.

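### Section 9.0 gives no IRB or other prompt route for serious events without physical harm or for non-serious unexpected events, and commits to no OT versus PL comparison of side effects

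*Combined protocol and SAP*

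**What the plan says.** Section 9.0 has three sentences, each with its own scope.

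- IRB: "Serious adverse events resulting in any physical harm associated with testing will be reported to the IRB", in line with whatever policies and guidance apply. The class must be serious, must involve physical harm and must be associated with testing. Expectedness is not a condition, and no time limit in days is given.
- DSMB: "Minor, and expected, adverse events (e.g. nausea, infusate infiltration, discomfort associated with infusion, nasal irritation") are the events that "will be reported to the Alcohol Studies DSMB meeting at least annually". The class must be both minor and expected.
- Publication and database: "Side effects attributable to the interventions will be reported in any manuscripts or scientific reports", and are also to be entered in any database that is mandated. There is no limit by seriousness, expectedness or physical nature, and no timing.

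Section 10.0 adds that the board "will review this study at least annually" and lists adverse event data, without restriction by class, among the items monitored. Section 11.0 lets the PI end a participant's participation on safety grounds but creates no reporting duty. Section 16.0 lists an adverse event reporting form whose content is not in the available text.

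**The concern.** The IRB rule is narrowed by the kind of harm, and the DSMB rule by severity and expectedness together. Whatever falls between the two has no stated route to prompt review. Two groups matter most. One is serious events that are psychological, not bodily. Section 4.2 excludes people who are actively suicidal or at serious suicidal risk, so the protocol itself treats psychiatric state as relevant to safety. The other is non-serious events nobody anticipated, which may be the first sign of a problem. For both, staff following the text would have no instruction to tell anyone before the next board review.

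A second, smaller matter concerns what is eventually published. The commitment covers side effects attributable to the interventions and says nothing about showing results by OT and PL session. Participants receive alcohol, or access to it, in both sessions, so attributing one symptom in one person to OT can be difficult. The blinded within-subject contrast is the better tool for that question, and the text does not commit to using it.

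**Working it through.** There is no stated figure to reproduce and no rate to compute. The check sorts events by seriousness, physical harm and expectedness, and reads each class against the stated routes.

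| Event class | IRB (9.0) | DSMB class named in 9.0 | Manuscript or mandated database (9.0) | General board review (10.0) |
|---|---|---|---|---|
| Serious, physical harm, associated with testing, expected or not | Yes, under applicable policies | Not named | If attributable, untimed | At least annual |
| Serious, no physical harm | No | Not named | If attributable, untimed | At least annual |
| Non-serious, unexpected | No | Not named | If attributable, untimed | At least annual |
| Non-serious, expected, more than minor | No | Not named | If attributable, untimed | At least annual |
| Minor and expected | No | Yes, at least annual | If attributable, untimed | At least annual |

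Rows two and three are the gap that matters. Row four is also unnamed in Section 9.0 but is of less concern, because those events are anticipated.

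**Timing.** The longest wait consistent with an at-least-annual review is about 12 months. Section 5.0 sets a minimum of 3 weeks between a participant's two sessions. One participant can therefore complete both sessions between two board reviews. Section 7.0 plans 10-15 completers from up to 30 recruits, but no accrual rate or start date is given. The share of the sample tested between reviews cannot be derived.

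**Side-effect data.** The inputs are in Sections 7.0 and 8.0.

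- Clamp arm: the questionnaire is in each battery (baseline, after OT/PL, start of clamp, end of clamp). That is 4 per session and 4 × 2 = 8 per completer.
- Self-administration arm: one before the first OT/PL dose, one just before self-administration starts, then every 20 minutes over 150 minutes. Since 150 / 20 = 7.5, about 7 fall within the period. That is about 2 + 7 = 9 per session and 9 × 2 = 18 per completer.

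The Section 12.0 hypothesis plan lists the Stop Signal task, subjective perceptions and craving, the Stroop test, the Alcohol Purchase Task and alcohol self-administration. Side effects are not among them. So the data for an OT versus PL comparison will exist in both arms, but neither Section 9.0 nor Section 12.0 commits to making it.

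**The case against.** The strongest reply is that other sources may fill the gap. IRB reporting is tied to applicable policies and guidance, which may require more. The appendix form may ask for more, and the monitoring plan in Section 10.0 covers adverse event data of every class. A technician monitors the participant throughout the infusion (Section 7.0), the PI can stop participation, and annual review is a minimum frequency. Part of this stands: the policies and the form cannot be checked here, and participants are observed. But the text invokes the policies only for the class already narrowed to physical harm, and observing or stopping a participant is not reporting. On the face of the documents the gap remains.

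Several stronger readings are tempting and are not supported:

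- *That unexpected events in general have no route.* The IRB sentence has no expectedness condition, so an unexpected serious event with physical harm from testing does reach the IRB.
- *That the annual review is the only route of any kind.* The manuscript and mandated-database sentence is a further route, though it is untimed and not a means of prompt oversight.
- *That the protocol's own claim of novelty signals unknown safety.* That remark, in the power discussion of Section 12.0, concerns OT's effect on laboratory measures and explains the lack of preliminary data. The same sentence calls OT commonly used in human studies.
- *That the attribution wording will hide an OT excess of alcohol-type symptoms.* The word interventions is plural and may include alcohol, so such events may still be reported. Attribution could also be made by comparing sessions. What can be said is only that the comparison is not promised.
- *That every serious event must go to the IRB whatever its cause.* Association with testing need not mean a causal verdict, and nothing in the documents requires the wider scope.
- *That most participants would be tested before the board looks.* Without an accrual rate this is unknown.

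**Conclusion.** The concern holds in a limited form. It is a restriction in the wording, not merely a missing detail: the physical-harm condition actively leaves out serious psychological events, and the minor-and-expected condition leaves out non-serious unexpected ones. For those two classes the only stated oversight may be about 12 months away. The absence of a commitment to compare side effects by session is a separate reporting weakness.

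The conclusion assumes that Section 9.0 is followed as written and that the unseen policies and form do not independently require prompt reporting of these classes. If they do, the practical gap is smaller and the protocol text should say so. Nothing here shows that any event has been or would be mishandled, and the efficacy analyses are unaffected.

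**What to change.** In Section 9.0:

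1. Delete the physical-harm limit, so that serious adverse events, physical or psychological, go to the IRB under the applicable policies.
2. State that unexpected events possibly related to study procedures go promptly to the IRB and to the DSMB chair under those policies.
3. Commit to reporting all recorded side effects by OT and PL session, without an attribution filter. Give the number of participants contributing to each session, and include those who attend only one, whom Section 12.0 drops from the final analyses. With 10-15 completers split across two arms, this table should be descriptive.

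The cost is a rewording of one section, a few more reports to the IRB and board, and one additional table from data already being collected. No visit, assessment or sample-size change is needed.

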5.0 Study Design

Overview: This project employs a double-blind, within-subject design. Each participant will be randomly assigned to either the clamp or self-administration condition, and be studied twice, once with intranasal administration of OT and once with intranasal PL. At least 3 weeks will elapse between each participant's tests to ensure that residual effects of OT administration have dissipated.

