Figure 3: Alcohol Clamp. Diagram of the experimental session showing test batteries (orange boxes), OT and PL administrations (green boxes), alcohol clamp (grey box) and example subject breath alcohol concentrations (colored lines). **Experimental timeline:** Min 0-30: Baseline battery. Min 30-35: Intranasal OT or PL administered. Min 35-60: Pause for drug absorption. Min 60-90: OT/PL battery. Min 90-105: OT/PL booster dose at the beginning of a 15 min alcohol infusion ramp (4 mg/dL/min) to bring BrAC to 60 mg/dL. Min 110-140: Alcohol+OT or Alcohol+PL battery assessing initial response to alcohol during BrAC clamp at 60 mg/dL. Min 180-182.5: Booster dose of OT or PL. Min 200-230: Alcohol+OT or Alcohol+PL battery assessing adapted response to alcohol during BrAC clamp at 60 mg/dL.

Session procedures: Alcohol Clamp (Figure 3). Clamp sessions begin with a baseline battery lasting approximately 30 min and consisting of the Stop Signal Task (a motor impulsivity task that has demonstrated sensitivity to alcohol exposure); a subjective perceptions assessment, including craving; a side effects questionnaire; the Alcohol Purchase Task (a cognitive test providing measures of behavioral economics, revised for use during iv infusion); and the Stroop Test of mental concentration (accuracy and speed stating the color of a series of words printed in colors different from the colors they actually name). The battery is repeated after an initial dose of OT or PL, and at the beginning and end of a 2 h clamp, with booster doses of OT or PL 20 min prior to each of the clamp batteries. The dosing schedule of oxytocin relative to testing is derived from studies suggesting onset of effects in approximately 30 minutes and a duration of approximately 60 minutes⁴⁸⁻⁵¹. The first dose of OT or PL will consist of 10 intranasal puffs [insufflations] alternating every 30 seconds between nostrils, delivering in total 40 IU of OT in 1 ml of solution or 1 ml of PL solution. A 20-30 min drug absorption period follows the first dose; booster doses of 24 IU of OT will be given 20 min prior to each of the remaining 2 test batteries. During the intervals between test batteries, the participant will be free to rest, read, or use an electronic device for entertainment.

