Session procedures: Self-administration (Figure 4). During the 150 min alcohol self-administration session, the participant initiates each work-set by choosing between 1 of 2 rewards, either alcohol or water. Work-sets consist of trials of the Constant Attention Task, or CAT (Figure 5), developed by our laboratory and with demonstrated sensitivity to pharmacogenomics and sex effects^{38, 39}. Successive rewards require an increasing number of successful CAT trials. The work schedules required to obtain water or alcohol are identical, but progress is tracked separately and not communicated to the participants. Throughout any workset, participants are free to wait, work ad-lib, pause, or cease working. The available rewards are a standardized increment in BrAC (alcohol, labeled "A") or an infusion of saline (water, labeled "W"), each delivered over 2.5 min. Reward delivery begins immediately after the last correct CAT trial required for the work-set is performed. Alcohol reward increments raise the participant's BrAC by 10.0 mg/dL in 2.5 min before declining at a steady rate of -0.8 mg/dl/min, until the next alcohol reward is delivered or as long as pharmacokinetically possible. CAIS continuously estimates the future time course of BrAC and prohibits infusion that would vield a BrAC exceeding the predetermined, ecologically valid safety limit (180 mg/dL in this heavy alcohol drinking sample). The first dose of OT or PL will be administered 30 min before the start of the self-administration phase, and consist of 10 intranasal puffs [insufflations] alternating every 30 seconds between nostrils, delivering in total 40 IU of OT in 1 ml of solution or 1 ml of PL solution. Booster doses of 24 IU of OT will be given approximately hourly after the initial dose. Participants will complete the subjective perceptions assessment and side effects questionnaire prior to the first OT/PL administration, immediately before the start of alcohol self-administration, and at 20 min intervals throughout the session, timed with alcohol reward increments when possible. Except for ad-libitum bathroom breaks, participants remain in the chamber or room for the duration of the experiment; technician interaction is limited to occasional BrAC samples, data collection, and verbal checks to assure subject comfort at the beginning/end of each intervention.

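### The commitment to publish side effects rests on an undefined attribution condition, and no oxytocin-versus-placebo summary of the side-effect data is planned

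*Combined protocol and SAP*

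**What the plan says.** Section 9.0 has three reporting routes.

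- Serious events: "Serious adverse events resulting in any physical harm associated with testing will be reported to the IRB".
- Minor and expected events, with nausea among the examples: these "will be reported to the Alcohol Studies DSMB meeting at least annually".
- Publications: "Side effects attributable to the interventions will be reported in any manuscripts or scientific reports based upon the collected data". The same sentence covers entry into any mandated database.

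The attribution condition stands only in the third route. Section 9.0 does not define it, and does not say who applies it, by what method, or whether before or after unblinding. Section 6.0 blinds subjects and technicians and is silent on this assessor.

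The data are richer than this commitment. Under Section 5.0 each participant will "be studied twice, once with intranasal administration of OT and once with intranasal PL". In the clamp arm the side effects questionnaire is part of the baseline battery, and "The battery is repeated after an initial dose of OT or PL, and at the beginning and end of a 2 h clamp". In the self-administration arm it is completed "prior to the first OT/PL administration, immediately before the start of alcohol self-administration, and at 20 min intervals throughout the session". The calendar in Section 8.0 agrees, marking the questionnaire in the baseline, OT/PL, clamp and self-administration columns.

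Section 12.0 plans paired t-tests of OT against PL. The measures it names are the Stop Signal task, subjective perceptions and craving, the Stroop test, the Alcohol Purchase Task and alcohol self-administration. Side effects are not among them. Its missing-data paragraph excludes from the final analyses anyone who completes only one of the two sessions.

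**The concern.** In a crossover with a placebo session, whether a complaint belongs to OT is best answered by comparing the same person's two sessions. That needs no causal opinion on individual events. The publication sentence instead makes reporting conditional on such an opinion, and no section promises the comparison.

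Two things are at stake. The first is tolerability. The study exists to support a larger trial, which will need to know what the spray does in people who are also receiving alcohol. Nausea can come from alcohol, so an OT excess of nausea could be put down to alcohol.

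The second is how the aims are read. Section 12.0 predicts slower responses and less work for alcohol under OT. A participant who feels unwell under OT could show the same pattern with no change in tolerance or motivation. A reader of the eventual report needs the side effects by session to weigh that explanation.

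**Working it through.** The plan states no side-effect rate, safety margin or safety sample size, so there is no figure to reproduce. The check has three parts.

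**1. Is the comparison available, and is it promised?**

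| Block | Clamp arm (7.0) | Self-administration arm (7.0) | OT-PL summary in 12.0 |
|---|---|---|---|
| Before the spray | Min 0-30 | Before first OT/PL dose | None |
| After the spray, before alcohol | Min 60-90 | Just before self-administration starts | None |
| Alcohol phase | Min 110-140 and 200-230 | Every 20 min | None |

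The data exist in both sessions for every block. The pre-alcohol block separates OT from alcohol cleanly, but only for the first dose. In the clamp arm the boosters come at the start of the alcohol ramp (min 90) and during the clamp (min 180). In the other arm they come roughly hourly after a first dose given 30 min before self-administration begins. Side effects after a booster are therefore observed with alcohol available or already infused, and the PL session is the comparator for them.

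**2. What can an attribution condition do to an OT-PL contrast?** The inputs here are assumptions, not documented figures: true rates of 40% (OT) and 20% (PL).

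Reported rate = true rate x share of events called attributable.

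| Share kept, OT / PL | Reported OT | Reported PL | Difference | Ratio |
|---|---|---|---|---|
| 100% / 100% | 0.40 | 0.20 | 0.20 | 2.0 |
| 50% / 50% | 0.40 x 0.5 = 0.20 | 0.20 x 0.5 = 0.10 | 0.10 | 2.0 |
| 25% / 25% | 0.40 x 0.25 = 0.10 | 0.20 x 0.25 = 0.05 | 0.05 | 2.0 |
| 60% / 40% | 0.40 x 0.6 = 0.24 | 0.20 x 0.4 = 0.08 | 0.16 | 3.0 |
| 40% / 60% | 0.40 x 0.4 = 0.16 | 0.20 x 0.6 = 0.12 | 0.04 | 1.33 |

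Equal shares, as a fully blind assessor might produce, leave the ratio alone and shrink the counts and the absolute difference. Unequal shares also move the ratio, in either direction. The documents do not say which case applies.

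**3. How much does a single event weigh here?** Section 7.0 plans 10-15 completers, with at least 5 per arm. With zero events in n people, the one-sided 95% upper bound on the rate is 1 - 0.05^(1/n):

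- n = 5: 45.1%
- n = 10: 25.9%
- n = 15: 18.1%

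These bounds come from the small sample, not from the attribution condition. They show that an empty row in the report would rule out little, so an observed event should not be left out on an opinion about its cause.

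**The case against.** The strongest reply is that the sentence sets a minimum. A reader might infer that all other side effects will be withheld, but the word *only* is not in the text and wider reporting remains open. That stands. What remains is that nothing wider is promised.

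Next, *interventions* is plural and may include the alcohol infusion. On that reading, nausea blamed on alcohol is still reported. This also stands, and it removes the scenario in which every such event disappears. It does not secure the comparison. With the assumed rates and 15 completers, 6 OT sessions and 3 PL sessions with nausea could be published as 9 of 30 sessions, with no split.

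A reader might also infer that attribution displaces a planned OT-PL safety comparison. It does not: Section 12.0 contains none, so the defect is an omission. Nor do the documents show that OT and alcohol effects can never be told apart. Both arms have a questionnaire after the spray and before alcohol, and attribution could in principle rest on the within-person difference. The difficulty is confined to events with alcohol on board that are attributed case by case.

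The oversight routes are sound as far as they go. Reporting to the IRB and DSMB does not depend on attribution to OT, and the DSMB's remit in Section 10.0 includes "outcome and adverse event data, assessment of scientific reports or therapeutic development". These routes do not reach readers of the published report.

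Finally, a reader might infer that data are lost or that the safety result is biased. Nothing is deleted: the questionnaires are collected in every block and Section 15.0 keeps records for 7 years. Bias is a possibility that depends on an assessor the plan does not describe.

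**Conclusion.** The point holds as a gap in planned reporting. The published and database record of side effects is guaranteed only for events meeting an undefined condition, and no OT-PL summary of the questionnaire is planned, although the crossover supplies one directly. Neither reading of *interventions* guarantees that summary.

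The risk is that an OT excess is understated, and that feeling unwell under OT, as a rival explanation for the Aim 1 and Aim 2 findings, goes unreported. Its size cannot be derived from the documents; the figures above rest on assumed rates and assumed retention shares. No efficacy calculation changes, only the evidence available for interpreting it. For an exploratory pilot with no stated safety objective this is a cheap improvement that should be made, not a flaw that undermines the study.

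One further consequence follows from the missing-data rule. If the single-session exclusion is carried over to safety, someone who leaves after an unpleasant first session would be in the published record only if the event met the attribution condition.

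**What to change.** Replace the publication sentence in Section 9.0 with a commitment to the following:

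- Report all side effects and adverse events from the first spray onward, whatever the presumed cause, in publications and in any mandated database.
- Tabulate them by session (OT, PL) and by block (after the spray before alcohol; alcohol phase), with within-person change from the pre-spray questionnaire.
- Include participants who completed only one session, shown under the session they received. They contribute to the counts but not to the paired OT-PL contrast.
- Show any attribution as an added column, naming who makes it, and record it before unblinding.
- In the self-administration arm, present the alcohol-phase comparison next to BrAC. Exposure there is self-selected, so the two sessions may differ in alcohol as well as in spray. The clamp arm has the same BrAC target in both sessions.

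The summary can be descriptive; no test is needed at this sample size. The cost is one rewritten sentence and one table, from data already collected. The downside is a longer table that includes ordinary alcohol effects.
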